9.16 ADVERSE EVENTS/SERIOUS ADVERSE EVENT CAUSALITY ASSESSMENT

The Investigator must also assess the relationship of any adverse event to the use of study drugs (whether none, one, or both), based on available information, using the following guidelines:

- **Not Related:** Clear-cut temporal and/or mechanistic relation to a cause other than the study drug(s).
- **Doubtful:** There is no reasonable possibility that the event is related to the study drug(s) but a definite cause cannot be ascertained.

- **Possible:** There is still a reasonable possibility that the cause of the event was the study drug(s) but there exists a more likely cause of the event such as complications of progressive disease.
- **Probable:** The most likely cause of the event is the study drug(s) but other causes cannot be completely excluded.
- **Definite:** Clear cut temporal and/or mechanistic relation to the study drug(s). All other causes have been eliminated. Events classified as definite will often be confirmed by documenting resolution on discontinuation of the study drug and recurrence upon resumption.

9.16.1 RECORDING OF ADVERSE EVENTS

All adverse events of any patient during the course of the study will be reported on the case report form, and the investigator will give his or her opinion as to the relationship of the adverse event to study drug treatment (i.e., whether the event is related or unrelated to study drug administration – TGR-1202). If the adverse event is serious, it should be reported as soon as possible and no greater than 24 hours to the sponsor or designee. Other untoward events occurring in the framework of a clinical study are also to be recorded as AEs (i.e., AEs that occur prior to assignment of study treatment that are related to a protocol-mandated intervention, including invasive procedures such as biopsies, medication washout, or no treatment run-in).

All AEs regardless of seriousness or relationship to study drug treatment spanning from Cycle 1/Day 1 until 30 calendar days after discontinuation or completion of protocol-specific treatment as defined by the protocol for that patient, are to be recorded on the eCRF.

9.16.2 ABNORMAL LABORATORY VALUES AND VITAL SIGNS

The reporting of abnormalities of vital signs as adverse events should be avoided. Abnormalities of vital signs should not be reported unless any criterion for an SAE is fulfilled, the vital signs abnormalities cause the patient to discontinue study treatment, or the investigator insists that the abnormality should be reported as an AE. Abnormal laboratory results should be noted in the eCRF as an adverse event if they are associated with an overdose, require or prolong inpatient hospitalization, or are otherwise considered clinically significant by the investigator. If an abnormal laboratory value or vital sign is associated with clinical signs and/or symptoms, the sign or symptom should be reported as an AE, and the associated laboratory value or vital sign should be considered additional information that must be collected in the relevant eCRF. If the laboratory abnormality is a sign of a disease or syndrome, only the diagnosis needs to be recorded on the SAE Report Form or AE eCRF.

Clinical Laboratory Results will be summarized. Summary statistics for actual values and for changes from baseline will be tabulated for laboratory results by scheduled visit. Patients with laboratory values outside of the normal reference range at any post-baseline assessment will be summarized, and graded per NCI CTCAE Version 4.0 when applicable. Patient incidence of abnormal laboratory results will be summarized by treatment group and maximum grade for each abnormal laboratory finding.

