5 STUDY ASSESSMENTS AND TREATMENT SCHEDULE

5.1 STUDY ASSESSMENTS AND TREATMENT SCHEDULE

Cycle = 28 days	Screen	Cycle 1 ₁			Cycles 2-6 ₂					> Cycle 6 ₃		End of Study	Follow-up
					C2	C3	C4	C5	C6	Every 3 Months			
Procedure\Days	-28-0	D1	D8	D15	Day 1					Day 1			Day 1
Medical History	X												
ECOG Performance Status	X	X			X	X	X	X	X	X	X	X	
Physical Examination ₄	X	X			X	X	X	X	X	X	X	X	
Vital Signs (pulse, BP, temp, weight)	X	X	X	X	X	X	X	X	X	X	X	X	
BM Aspirate/Biopsy ₅	X												
12-lead EKG	X												
Tumor Evaluation ₆	X				Every 3 cycles								
Serology: HCV, HBV, CMV ₇	X												
Hematology ₈	X	X	X	X	X	X	X	X	X	X	X	X	
Serum Chemistry	X	X	X	X	X	X	X	X	X	X	X	X	
PT/INR	X				As clinically warranted								
Serum Pregnancy Test ₉	X												
Concomitant Medications	X	X	X	X	X	X	X	X	X	X	X	X	
AE Evaluation ₁₀	X	X	X	X	X	X	X	X	X	X	X	X	
LTFU ₁₁												X	
TGR-1202					Administered orally daily with food								

¹ Treatment Administration +/- 1 day window. Physical Exam, Vital Signs, ECOG PS, Hematology and Serum Chemistry visit days have - 1 day window

² Treatment Administration +/- 3 day window. Physical Exam, Vital Signs, ECOG PS, Hematology and Serum Chemistry visit days have a - 3 day window during Cycles 2 through 6.

³ Treatment Administration +/- 7 day window. Physical Exam, Vital Signs, ECOG PS, Hematology and Serum Chemistry visit days have a - 7 day window for all cycles after cycle 6.

⁴ To include assessment of B-symptoms

⁵ Unilateral bone marrow aspirate and/or biopsy should be completed within 90 days prior to Day 1 of Cycle 1 as clinically indicated per standard of care. In addition, a post-baseline bone marrow biopsy should be completed to confirm potential CR by radiological assessment.

⁶ Scans should be completed within 30 days prior to Day 1 of Cycle 1. All tumor evaluations have a +/- 7 day window. Radiology assessment should include FDG-PET and/or a contrast enhanced CT scan of chest, abdomen, and pelvis. If iodinated contrast is contraindicated, a non-contrast chest CT coupled with a gadolinium-enhanced MRI of the abdomen/pelvis is an acceptable substitute. For Waldenstrom's macroglobulinemia evaluation should include immunofixation and serum electrophoresis. For patients with WM without nodal involvement, response will be assessed by quantitative monoclonal IgM protein every 3 cycles

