7.1.1.3 UNCOMMON (≥1 - <10%)

- **Blood and Lymphatic System Disorders:** Anemia, Febrile neutropenia, Leukocytosis, Thrombocytopenia
- **Eye Disorders:** Vision Blurred

- **Gastrointestinal Disorders:** Abdominal distension, Abdominal pain, Constipation, Dry mouth, Dyspepsia, Colitis
- **General Disorders and Administration Site Conditions:** Asthenia, Chills, Oedema peripheral, Pyrexia
- **Infections and infestations** Oral candidiasis, Pneumonia, Upper respiratory tract infection
- **Investigations:** Alanine aminotransferase increased, Aspartate aminotransferase increased, Blood creatinine increased, Lymphocyte count increased, Weight decreased
- **Metabolism and Nutrition Disorders:** Dehydration, Hyperglycemia, Hypokalemia, Hypophosphatemia,
- **Musculoskeletal and Connection Tissue Disorders:** Arthralgia, Muscle spasms, Pain in extremity
- **Nervous System Disorders:** Dizziness, Dysgeusia, Headache, Neuropathy peripheral, Tremor
- **Psychiatric Disorders:** Insomnia
- **Respiratory, Thoracic and Mediastinal Disorders:** Cough
- **Skin and Subcutaneous Tissue Disorders:** Alopecia, Night sweats, Pruritus

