9.12 SAFETY ANALYSES

Safety evaluations will be based on the incidence, intensity, and type of adverse events, as well as on clinically significant changes in the patient's physical examination, vital signs, and clinical laboratory results. Safety analyses will be performed using the safety population. Exposure to study treatment and reasons for discontinuation of study treatment will also be tabulated.

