9.14 DEFINITIONS OF ADVERSE EVENTS

An adverse event (AE) is any untoward medical occurrence in a patient or clinical investigation patient administered a pharmaceutical product. An AE does not necessarily have to have a causal relationship with this treatment. An adverse event (AE) can therefore be any unfavorable and unintended sign (including an abnormal laboratory finding, for example), symptom, or disease temporarily associated with the use of a medicinal product, whether or not considered related to the medicinal product. This includes any occurrence that is new in onset or aggravated in severity or frequency from the baseline condition.

In clinical studies, an AE can include an undesirable medical condition occurring at any time, including run-in or washout periods, even if no study treatment has been administered. The NCI Common Terminology Criteria for Adverse Events (CTCAE) v4.0 is to be used for the grading of severity of symptoms and abnormal findings. For adverse events not covered by the NCI-CTCAE Version 4.0 grading system, the following definitions will be used:

- **Grade 1:** Mild; asymptomatic or mild symptoms; clinical or diagnostic observations only; intervention not indicated.
- **Grade 2:** Moderate; minimal, local or non-invasive intervention indicated.
- **Grade 3:** Severe or medically significant but not immediately life-threatening; hospitalization or prolongation of hospitalization indicated.
- **Grade 4:** Life-threatening consequences; urgent intervention indicated.
- **Grade 5:** Death related to AE.

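### Section 9.16.2 discourages recording vital-sign abnormalities as AEs, in conflict with Sections 9.14 and 9.16.1, so isolated non-serious fever, weight loss or blood pressure change may be under-recorded

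*Combined protocol and SAP*

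**What the plan says.** Section 9.16.2 opens with the instruction "The reporting of abnormalities of vital signs as adverse events should be avoided". The next sentence makes it a default with exceptions: "Abnormalities of vital signs should not be reported unless any criterion for an SAE is fulfilled", or the abnormality causes the patient to stop study treatment, or "the investigator insists that the abnormality should be reported as an AE".

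The same section treats laboratory values differently. They become AEs if linked to an overdose, if they require or prolong hospitalization, or if the investigator simply considers them clinically significant. It then adds a rule for both kinds of finding: where an abnormal value comes with signs or symptoms, the sign or symptom is the AE and the value is collected as supporting information. Section 9.20.2 repeats the laboratory rule and the symptom rule, but not the instruction to avoid vital-sign AEs.

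Elsewhere:
- Section 9.14 counts as an AE "any unfavorable and unintended sign (including an abnormal laboratory finding, for example), symptom, or disease".
- Section 9.16.1 requires all AEs from Cycle 1/Day 1 to 30 days after treatment to be recorded, regardless of seriousness or causality.
- Section 9.12 rests the safety evaluation on AEs and also on "clinically significant changes in the patient's physical examination, vital signs, and clinical laboratory results".
- The schedule in Section 5.1 has the row "Vital Signs (pulse, BP, temp, weight".
- Section 7.1.1.3 lists "Asthenia, Chills, Oedema peripheral, Pyrexia" and "Blood creatinine increased, Lymphocyte count increased, Weight decreased" among events seen with the single agent, considered at least possibly related, at 1% to under 10%.

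**The concern.** Take a patient with a clinically significant fever, weight loss or blood pressure change that is not serious, does not stop treatment and has no accompanying symptom. Sections 9.14 and 9.16.1 make it a recordable AE. Section 9.16.2 tells the site not to record it unless the investigator overrides the default. A site cannot follow both, and two sites could reasonably resolve the conflict in different ways.

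Safety is a key secondary objective, and the protocol's rationale for the drug leans on better tolerability than another inhibitor of the same class. With one arm, AE incidence will be read on its own or against outside rates. Under-recording would make the drug look better tolerated, and no control arm would share the error. A later SAP can add tables, but it cannot create AE records, with their causality and seriousness assessments, that sites were told not to make.

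**Working it through.** The plan gives no figure on this point, so there is none to reproduce. The check compares the text and then gives a rough scale.

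**Step 1: the rules side by side.**

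| Finding (non-serious, no symptom, treatment continues) | 9.14 and 9.16.1 | 9.16.2 |
|---|---|---|
| Laboratory value judged clinically significant | AE, recorded | AE, recorded |
| Vital sign judged clinically significant | AE, recorded | Not reported unless the investigator insists |

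The first row agrees and the second does not. The exceptions in 9.16.2 also cover stopping treatment but not delaying or reducing it, so a vital-sign abnormality could prompt a dose change without having its own AE record.

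**Step 2: which listed events are exposed.** Temperature and weight are vital signs in Section 5.1. Pyrexia and weight decreased are named in Section 7.1.1.3. Blood pressure and pulse fall under the same rule.

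**Step 3: what still reaches the data.** AE records remain for serious events, abnormalities that stop treatment, cases where the investigator insists, and symptomatic cases (through the symptom). Section 9.2 says the listings will hold all available safety data, so the readings themselves are kept. The exposed group is therefore isolated, non-serious, clinically significant readings in patients who continue treatment.

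**Step 4: scale.** Inputs: n = 20 MZL + 20 WM = 40 at most (synopsis, Statistical Considerations), and p from 1% to just under 10% (Section 7.1.1.3; 9.99% is used for the upper end). The share f of cases lost is not in the documents and is assumed over its whole range.

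Expected recorded cases = 40 × p × (1 − f). With f = 0: 40 × 0.01 = 0.4, and 40 × 0.0999 ≈ 4.0.

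P(at least one recorded) = 1 − (1 − p(1 − f))^40. With f = 0: 1 − 0.99^40 = 33.1%, and 1 − 0.9001^40 = 98.5%.

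| Share lost (assumed) | Expected recorded cases per term | P(at least one recorded) |
|---|---|---|
| 0% | 0.4 to 4.0 | 33.1% to 98.5% |
| 25% | 0.3 to 3.0 | 26.0% to 95.6% |
| 50% | 0.2 to 2.0 | 18.2% to 87.1% |
| 75% | 0.1 to 1.0 | 9.5% to 63.6% |
| 100% | 0 | 0% |

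Within one histology group of 20, full reporting gives 0.2 to 2 cases per term.

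These counts indicate scale only. The listed frequencies are for events at least possibly related to the drug, whereas Section 9.15 tabulates treatment-emergent AEs of any cause. They also do not separate isolated cases from symptomatic ones.

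**Step 5: is there a vital-sign analysis?** Section 9.16.2 specifies by-visit summaries and CTCAE grading for laboratory results. No section of this document specifies a counterpart for vital signs.

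**The case against.** The strongest reply is that little is actually lost. The investigator has the last word, since any abnormality can be reported by insisting on it. Symptomatic cases enter through the symptom. Section 9.20 records AEs in the patient's own words or as a diagnosis, so a fever the patient complains of, or one due to an infection, has another route in. Table 1 handles neutropenic fever by name. The readings are taken at every scheduled visit and will be listed, Section 9.2 gives general summary conventions, and Section 9 defers detail to a formal SAP that is not in the text reviewed. The study is descriptive, and Section 9.11 says no formal claims will be made.

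Much of this stands, and it narrows the exposed group. Two things survive it. Insisting is an override of a stated default, not the ordinary clinical-significance test that laboratory values receive. And a listed reading is not an AE: it carries no causality or seriousness assessment and does not enter the treatment-emergent tables.

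A reader might go further and infer that Section 9.16.2 contradicts Section 9.12. It does not. Section 9.12 names vital-sign changes as a basis separate from AEs, and keeping a reading off the AE page leaves that basis intact. The gap is only that this document specifies no summary to deliver it, which the SAP could still supply.

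**Conclusion.** The conflict between Section 9.16.2 and Sections 9.14 and 9.16.1 is in the text and depends on no assumption. The passages must be reconciled. The consequence is a risk: isolated, non-serious, clinically significant changes in temperature, weight, blood pressure or pulse that do not stop treatment may be missing from the treatment-emergent AE tables.

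A reader might infer that pyrexia and weight loss are in fact undercounted, perhaps by half or more. The documents do not support that. They give no share of cases that are isolated and no share that investigators would leave out, so a figure of that kind would only repeat its own assumption. What can be said is that about 0.4 to just under 4 cases per term are expected in up to 40 patients, with an unknown loss of 0% to 100%. At counts this small, one or two missing records could remove a term from the tables.

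The point does not touch the response-rate analysis. It bears on how far the tolerability results can be relied on, and it is worth correcting because the correction is cheap and the missing AE records cannot be rebuilt later.

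**What to change.** Replace the first two sentences of Section 9.16.2 with the test already used there for laboratory values: a vital-sign abnormality is reported as an AE if the investigator considers it clinically significant, if it meets an SAE criterion, or if it leads to discontinuation of study treatment. Leave the rule on accompanying signs and symptoms as it is. This belongs in the protocol, because it governs what sites record.

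In Section 9.12 or the SAP, specify a summary of the vital signs already collected, so that the analysis promised in Section 9.12 has a defined output.

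Cost: one wording change and one extra table, with no new assessments. The downside is a few more low-grade AE records.

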	
 • To evaluate the overall response rate (CR + PR + VGPR + MR) and duration of response of TGR-1202 in patients with relapsed or refractory non-follicular indolent non-Hodgkin's lymphoma. 
KEY SECONDARY OBJECTIVES
 
 • To determine the progression free survival of TGR-1202 in patients with relapsed or refractory non-follicular indolent non-Hodgkin's lymphoma • To evaluate Time to Treatment Failure with TGR-1202 • To evaluate the safety profile of TGR-1202 
[REDACTED]
 
[REDACTED]
 
[REDACTED]

Inclusion Criteria	
Patients must meet all of the following inclusion criteria to be eligible for participation in this study:
 
 1. Histologically confirmed diagnosis of B-cell non-follicular indolent non-Hodgkin's Lymphoma meeting at least one of the two following requirements: 
 a. World Health Organization 2008 classification criteria warranting therapy as per investigator discretion for histologies limited to splenic marginal zone lymphoma (SMZL), nodal marginal zone lymphoma (NMZL), or extra-nodal marginal zone lymphoma (ENMZL), and lymphoplasmacytic lymphoma. b. Presence of CD20⁺ lymphoplasmacytic lymphoma involving the bone marrow, positive serum immunofixation for monoclonal IgM and at least one criteria for initiation of treatment as per Consensus panel of International Workshops on Waldenstrom's macroglobulinemia. 2. Relapsed or refractory after at least one prior treatment regimen, with no limit on prior therapies. 3. At least 1 measurable disease lesion >1.5 cm in at least one diameter by CT/CT-PET or magnetic resonance imaging (MRI) in an area of no prior radiation therapy, or in an area that was previously irradiated that has documented progression. 
 a. Exception included for Waldenstrom's macroglobulinemia patients without nodal involvement. 4. Waldenstrom's macroglobulinemia patients must have measurable quantitative IgM monoclonal protein greater than normal value. 5. Adequate organ system function, defined as follows: 
 a. Absolute neutrophil count (ANC) > 1,000 / platelet count > 50,000. b. Total bilirubin ≤1.5 times the upper limit of normal (ULN) c. Alanine aminotransferase (ALT) and aspartate aminotransferase (AST) ≤2.5 x ULN if no liver involvement or ≤5 x the ULN if known liver involvement

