3.1 INCLUSION CRITERIA

Patients must meet all of the following inclusion criteria to be eligible for participation in this study:

1. Histologically confirmed diagnosis of B-cell non-follicular indolent non-Hodgkin's lymphoma meeting following requirements.
 - a. World Health Organization 2008 classification criteria warranting therapy as per investigator discretion for histologies limited to splenic marginal zone lymphoma (SMZL), nodal marginal zone Lymphoma (NMZL), or extra-nodal marginal zone lymphoma (ENMZL), and lymphoplasmacytic lymphoma.
 - b. Presence of CD20⁺ lymphoplasmacytic lymphoma involving the bone marrow, positive serum immunofixation for monoclonal IgM and atleast one criteria for initiation of treatment as per Consensus panel of International Workshops on Waldenstrom's macroglobulinemia.
2. Relapsed or refractory after at least one prior treatment regimen, with no limit on prior therapies.
3. At least 1 measurable disease lesion >1.5 cm in at least one diameter by CT/CT-PET or magnetic resonance imaging (MRI) in an area of no prior radiation therapy, or in an area that was previously irradiated that has documented progression.
 - a. Exceptions include for Waldenstrom's macroglobulinemia patients without nodal involvement.
4. Waldenstrom's macroglobulinemia patients must have measurable quantitative IgM monoclonal protein greater than normal value.
5. Adequate organ system function, defined as follows:
 - a. Absolute neutrophil count (ANC) \geq 1,000 / platelet count \geq 50,000.
 - b. Total bilirubin \leq 1.5 times the upper limit of normal (ULN)
 - c. Alanine aminotransferase (ALT) and aspartate aminotransferase (AST) \leq 2.5 x ULN if no liver involvement or \leq 5 x the ULN if known liver involvement
 - d. Calculated creatinine clearance >30 mL/min (as calculated by the Cockcroft-Gault or MDRD formula, 24- hour urine Cr clearance also acceptable)
6. ECOG performance status \leq 2
7. Male or female \geq 18 years of age
8. Ability to swallow and retain oral medication
9. Female patients who are not of child-bearing potential and female patients of child-bearing potential who have a negative serum pregnancy test within 3 days prior to Cycle 1, Day 1.
10. Willingness and ability to comply with trial and follow-up procedures, and give written informed consent

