9.15 ADVERSE EVENTS (AE'S) AND TREATMENT EMERGENT ADVERSE EVENTS (TEAE'S)

All AEs and SAEs occurring on study will be listed by patient. The frequency and percentages of patients with treatment-emergent adverse events (TEAEs) will be tabulated by system organ class (SOC) and preferred term (PT), where treatment-emergent is defined as any AE that:

- Occurs after first dosing of study medication and through the end of the study or up through 30 days after the last dose of study treatment, or
- Is considered treatment-related regardless of the start date of the event, or
- Is present before first dosing of study medication but worsens in intensity or the investigator subsequently considers treatment-related.

TEAEs that are considered at least possibly related to study treatment will be tabulated as well as deaths, SAEs, and events resulting in treatment discontinuation.

AEs that occur after informed consent but before first dosing of study medication will not be summarized but will be listed.

At each level of summarization, a patient will be counted only once for each AE, SOC, or PT experienced within that level. In the summation for AE severity, within each level of AE, SOC, or PT experienced, the one with the highest severity will be included. In the summation for AE's relationship to the study drug, within each level of AE, SOC, or PT experienced, the one with the closest relationship to the study drug will be included.

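### The graded laboratory table (Section 9.16.2) uses maximum post-baseline grade without each patient's baseline grade, so it cannot separate unchanged entry abnormalities from new or worsening ones.

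*Combined protocol and SAP*

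**What the plan says.** Section 9.16.2 plans three laboratory outputs.

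- Values by visit: "Summary statistics for actual values and for changes from baseline will be tabulated for laboratory results by scheduled visit".
- Who counts as abnormal: "Patients with laboratory values outside of the normal reference range at any post-baseline assessment will be summarized", with CTCAE v4.0 grading where it applies.
- How incidence is shown: "Patient incidence of abnormal laboratory results will be summarized by treatment group and maximum grade for each abnormal laboratory finding".

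The second and third define the graded table. Their only time reference is post-baseline; the baseline grade plays no part.

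Eligibility lets patients enter with abnormal values. The synopsis requires "Absolute neutrophil count (ANC) > 1,000 / platelet count > 50,000" (Section 3.1 writes the same limits as at-least), and "Alanine aminotransferase (ALT) and aspartate aminotransferase (AST) ≤2.5 x ULN if no liver involvement or ≤5 x the ULN if known liver involvement". Bilirubin may be up to 1.5 × ULN. Criterion 5 sets no limit for hemoglobin or lymphocytes.

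For adverse events the protocol does look back to baseline. Under Section 9.15 an event is treatment-emergent if, among other routes, it "Is present before first dosing of study medication but worsens in intensity". Section 9.20.5 records a pre-existing condition as an adverse event only if it worsens. Neither rule is extended to the laboratory grades.

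**The concern.** The trial has one arm, so no control group shows how often abnormal values would be seen without the drug. Each patient's own baseline is the only available reference, and the graded table does not use it.

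Two kinds of information are lost. First, someone who enters with ALT at 2.4 × ULN and stays there is counted as a post-baseline abnormality. Second, a patient who rises to a given grade falls in the same cell as one who was at that grade all along, so a real change can be hidden as easily as an unchanged value can be added.

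The safety profile is a secondary objective (Section 2.1). The study rationale rests partly on tolerability, citing neutropenia as the only Grade ≥3 event above 10% and minimal transaminitis. Neutrophils and transaminases are among the analytes for which entry abnormality is allowed. Section 6.3 itself recognizes that cytopenias may come from the underlying disease. Results are to be shown by histology with up to 20 patients each, so one patient is worth at least 5 points (1/20). Different baseline rates in MZL and WM would then look like different on-study rates.

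**Working it through.** The plan has no figure of its own to reproduce here. The check has two parts.

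**1. Does any other text change who enters the graded table?**

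| Section | What it does | Effect on the graded table |
|---|---|---|
| 9 (opening) | Defers derivations and safety methods to a later SAP | None in the text available |
| 9.2 | Listings of all available data | None; patient-by-patient reading only |
| 9.12 | Bases safety evaluation on clinically significant laboratory changes | None; gives no grade rule |
| 9.15 | Treatment-emergent rule for adverse events | None; covers adverse events |
| 9.16.2 | Change from baseline by visit | None; group statistics on values, not grades |
| 9.20.5 | Pre-existing conditions | None; covers AE/SAE recording |

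Hematology and chemistry are drawn at Screening, on Days 1, 8 and 15 of Cycle 1, on Day 1 of Cycles 2–6, and every 3 months after that (Section 5.1). With this many samples, an any-visit maximum will almost always pick up an abnormality that persists from entry.

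**2. How large could the effect be?**

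Inputs:
- n: up to 20 MZL + up to 20 WM = up to 40 (synopsis).
- b: share entering with an abnormality that persists. Not in the documents; assumed 10–40%.
- e: share with a true grade worsening on study, independent of b. Not in the documents; assumed 0–30%.

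Formulas for the any-grade row:
- Planned incidence = b + (1 − b) × e
- Treatment-emergent incidence = e
- Excess = b + (1 − b) × e − e = b × (1 − e)

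| b | e | Planned | Treatment-emergent | Excess (points) |
|---|---|---|---|---|
| 10% | 0% | 10% | 0% | 10 |
| 10% | 15% | 23.5% | 15% | 8.5 |
| 10% | 30% | 37% | 30% | 7 |
| 25% | 15% | 36.25% | 15% | 21.25 |
| 40% | 0% | 40% | 0% | 40 |
| 40% | 30% | 58% | 30% | 28 |

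The range is 0.10 × 0.70 = 7 points to 0.40 × 1.00 = 40 points. In a full cohort of 40 that is 2.8 to 16 patients. The upper end needs e = 0, meaning that nobody worsens. Patients whose abnormality resolves before the first post-baseline sample are not in b and add nothing.

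**By grade.** The entry limits cap how abnormal neutrophils, platelets, transaminases and bilirubin can be at baseline, so for these the excess falls mainly in the lower grades. The documents do not reproduce the CTCAE cut-points, so no exact grade is assigned here. Hemoglobin and lymphocytes have no stated entry limit and so no such cap.

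**The case against.** The strongest reply is that Section 9.16.2 describes abnormal laboratory results and never calls them toxicity or drug effect. Attribution is handled in Section 9.15, through treatment-emergent events and events at least possibly related. A laboratory value becomes an adverse event only under the conditions in Sections 9.16.2 and 9.20.2, and an unchanged pre-existing condition is not recorded as one. All of this stands. A reader might infer that the plan overstates drug toxicity, or that the adverse event tables are inflated; the documents support neither. Nor does Section 9.15 make worsening the sole test for a pre-existing event, since it also admits events that the investigator considers treatment-related.

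Baseline is also not absent from the plan as a whole. There are visit-level changes and full listings, and with at most 40 patients the listings can be read. This mitigates in part, but neither output gives the incidence of worsening or shows baseline grade against worst grade.

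The SAP may still settle the matter, since Section 9 defers detail to it. That too is fair. However, Section 9.16.2 already states a counting rule, and nothing in the available text modifies it.

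Finally, Section 9.11 makes no formal claims, and no decision rule in the text uses this table. That limits the consequence to how descriptive safety results are read.

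**Conclusion.** The point holds for the graded laboratory table only. As written, that table counts abnormalities present at entry that do not worsen, and cannot distinguish them from new or worsening ones. The any-grade excess over treatment-emergent incidence is b × (1 − e), or 7 to 40 points over the assumed ranges. Both inputs are assumptions, as is their independence, so the range illustrates the mechanism and does not predict the result.

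A reader might take 10 to 40 points as the expected excess. Those are the figures for e = 0; with e = 30% the same values of b give 7 to 28. A reader might also infer a sizeable effect on Grade ≥3 rows through hemoglobin, which has no explicit entry limit. The documents give no baseline hemoglobin data, and exclusion criterion 8 (severe or uncontrolled conditions) might keep some such patients out, so no figure can be put on that row.

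**What to change.** Keep the worst-grade table; it is informative as a description. Add to the SAP, before database lock:

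1. Laboratory baseline is the last value before the first dose.
2. A laboratory abnormality is treatment-emergent if its CTCAE grade rises by at least one from baseline. Report this incidence by maximum grade.
3. For each graded analyte, give a shift table of baseline grade by worst post-baseline grade.
4. Present these by histology and overall, in line with Section 9.2. The reference to treatment group in Section 9.16.2 does not fit a single-arm study and should be changed to match.

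The cost is a few additional standard tables. Screening and Cycle 1 Day 1 samples are already scheduled, so no new data are needed.
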